At each subsequent tumor assessment, the sum of diameters of target lesions identified at baseline plus the sum of diameters of up to 10 (maximum 5 per organ) new measurable lesions per timepoint (for which the longest diameter is ≥ 10 mm for non-nodal lesions or the short axis is ≥ 15 mm for non-nodal lesions) are added together to provide the total tumor burden. If more than 10 new measurable lesions total (or 5 per organ) at a given timepoint are present, the new measurable lesions should be selected on the basis of their size and suitability for accurate repeated measurements by imaging techniques (CT or MRI). If there are lesions beyond the new measurable lesion limit during the course of the study for one subject, the additional lesions would be considered new non-measurable lesions.

Tumor Burden = sum of diameter of target lesions + sum of diameter of new measurable lesions.

Non-target disease measurements are not required and these lesions should be followed as “present”, “absent”, or “unequivocal progression”.

For non-nodal target lesions that become too small to measure, a value of 5 mm will be assigned. If the non-nodal lesion subsequently increases in size to greater than or equal to 5 mm in one dimension, its true size will be recorded. If an actual measurement is able to be provided, this should be recorded even if it is <5 mm. If it is in the opinion of the radiologist that the non-nodal lesion has likely disappeared, the measurement should be recorded as “0 mm”. Nodal disease should always have the actual short axis measurement recorded even if the nodes regress to below 10 mm on study.

Response Evaluation:

Evaluation of Objective Response:

The subject response will be assessed based on tumor burden (the sum of diameters of target lesions plus the sum of up to 10 [maximum 5 per organ] new measurable lesions per timepoint), and, in the case of complete response (CR), the presence of any non-target and/or new non-measurable lesions. The overall response is derived from timepoint response assessments as described in [Table 6](#) and [Table 7](#).

Approved

Table 6. Definition of Measurable Tumor Response (Baseline Target and New, Measurable Lesions)

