Complete Response (CR):	Disappearance of all lesions (whether measurable or not and whether baseline or new) and confirmation by a repeat, consecutive assessment no less than 4 weeks (28 days) from the date first documented. Any pathological lymph nodes (whether target or non-target) must have reduction in short axis to < 10 mm.
Partial Response (PR):	Decrease in tumor burden ^a \geq 30% relative to baseline confirmed by a consecutive assessment at least 4 weeks (28 days) after first documentation
Progressive Disease (PD):	Increase in tumor burden ^a \geq 20% and at least 5 mm absolute increase relative to nadir (minimum recorded tumor burden) confirmation by a repeat, consecutive assessment no less than 4 weeks (28 days) from the date first documented PD.
Stable Disease (SD):	Neither sufficient shrinkage to qualify for CR or PR nor sufficient increase to qualify for PD.
Unable to Evaluate (UE):	Any lesion present at baseline which was not assessed or was unable to be evaluated leading to an inability to determine the status of that particular tumor for that time point.
Not Applicable (NA)	No target lesions were identified at baseline
Not Done (ND)	Radiographic imaging was not performed at this time point to evaluate the response of measurable lesions

^a Tumor Burden = sum of diameter of target lesions + sum of diameter of new measurable lesions.

Diameters used:

- For nodal disease, shortest axis
- For non-nodal disease, longest diameters

Approved

Table 7. Matrix for Determining the Overall Response at Each Assessment Point

Measurable Response	Non-measurable Response		Overall Response
Target and new, measurable lesions (tumor burden) ^a , %	Non-target	New, nonmeasurable lesions	Using irRC-RECIST
↓100 ^b	Absent/NA ^c	Absent	CR ^d
↓100	Present/ND/UE	Any	PR ^d
↓100	Unequivocal progression	Any	PR ^d
↓≥ 30	Absent/Present NA ^c /ND/UE	Any	PR ^d
↓≥ 30	Unequivocal progression	Any	PR ^d
↓< 30 to ↑< 20	Absent/Present/NA ^c /ND/UE	Any	SD
↓< 30 to ↑< 20	Unequivocal progression	Any	SD
↑≥ 20 ^e	Any	Any	PD
UE ^g	Any	Any	UE
ND ^g	Any	Any	UE
NA ^f	Any	Any	UE

CR = complete response; PR = partial response; SD = stable disease; PD = progressive disease; UE = unevaluable; ND = not done; NA = not applicable; irRC-RECIST = immune-related response criteria simulating Response Evaluation Criteria in Solid Tumors (RECIST)

^a Disease relative to baseline, including new measurable lesions only (> 10 mm).

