^b Disappearance of all non-lymph node lesions and all lymph nodes < 10 mm in short axis would also be CR even if lymph node measurements prevent 100% tumor burden reduction.

^c No non-target lesions identified at baseline.

^d Assuming response (CR or PR) or progression are confirmed by a second, consecutive assessment at least 4 weeks (28 days) apart.

^e In addition to relative increase of ≥ 20%, the tumor burden must also demonstrate an absolute increase of ≥ 5 mm from nadir for PD.

^f No target lesions identified at baseline. When a subject has only nonmeasurable disease (ie, no target lesions identified at baseline) the response will be (UE) unevaluable.

^g If one or more target/new measurable lesions are unevaluable or not measured but the sum of all evaluable target/new lesions measured show a ≥ 20% and at least 5 mm absolute increase relative to nadir, then the visit overall Target Response will be PD.

Determination of best overall response is based on changes in total tumor burden from the baseline (nadir, for PD) tumor assessment, regardless of any initial increase in baseline lesions or the appearance of new lesions.

Subjects are considered to have partial response (PR) or stable disease (SD) even if new lesions were present, as long as they met the respective thresholds of response as described in [Table 7](#).

A best overall response of SD requires a visit response of SD or better no earlier than 49 days after the date of enrollment; otherwise the overall response will be UE.

Approved

Confirmation of Response (CR or PR):

To be assigned a status of CR or PR changes in tumor measurements must be confirmed by consecutive repeat assessments performed no less than 4 weeks (28 days) after the criteria for response are first met.

In some circumstances it may be difficult to distinguish residual disease from normal tissue. When the evaluation of CR depends on this determination, it is recommended that the residual lesion be investigated (ie, biopsy) to confirm the CR status.

Confirmation of Disease Progression:

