For any target lymph node that is fully resected (and previously present ≥ 15 mm) and contained cancer or pathology results were unknown, 0 mm should not be recorded. In the event a measurement is not available, a 10 mm short axis should be reported.

For any target lymph node that is fully resected (and previously present ≥ 15 mm) and contained no cancer under pathology evaluation, 0 mm should not be recorded. In the event a measurement is not available, a 9 mm short axis should be reported.

Non-target lymph node previously present

For any non-target lymph node that is fully resected and contained cancer or pathology results were unknown, “present” should always be reported.

For any non-target lymph node that is fully resected and contained no cancer under pathology evaluation, “absent” should always be reported.

Lymph node not previously present

If a new lymph node was fully resected, measured and contained cancer or pathology results were unknown, it should be reported as a new non-measurable lymph node if its short axis was < 15 mm or, if it was ≥ 15 mm, it should be reported as a new measurable lymph node with a short axis of 10 mm.

If a new lymph node was fully resected, not measured and contained cancer or pathology results were unknown, it should be reported as a new non-measurable lymph node.

The initial dimension of a new measurable lymph node or presence of a new non-measurable lymph node should be reported at all subsequent assessments.

For any new lymph node that is fully resected and contained no cancer under pathology evaluation, it should not be recorded as either a target or non-target lesion. The full resection should only be reported on the Procedures eCRF.

Approved

Merging Lesions

When two or more target/new measurable lesions merge, the smaller lesion should have 0 (zero) mm recorded for the current and all future assessments, and the larger lesion should have the longest diameter of the merged lesion recorded for the current assessment and be followed for future assessments. When two or more non-target/new non-measurable lesions merge, the smaller lesion should be recorded as “absent” for the current and all future assessments, and the larger lesion should be recorded as “present” for the current assessment and followed for future assessments.

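### Protocol Appendix D, Table 7 refers the 20% increase for progression to baseline, while Table 6 and the surrounding text refer it to nadir, so one complete scan can be PR or SD by one table and PD by the other

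*Protocol*

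**What the plan says.** Appendix D derives the overall response from Tables 6 and 7 together and does not say which governs if they differ.

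- **Table 7, footnote a**, attached to the tumor-burden column: "Disease relative to baseline, including new measurable lesions only (> 10 mm". The CR, PR, SD and PD rows are percentage changes in that column.
- **Table 7, footnote e**, on the PD row: beyond the 20% relative increase, "the tumor burden must also demonstrate an absolute increase of ≥ 5 mm from nadir for PD". It names no reference for the 20% itself.
- **Table 7, footnote g**, for visits with unevaluable or unmeasured lesions, asks for a 20% increase and "at least 5 mm absolute increase relative to nadir, then the visit overall Target Response will be PD".
- **Table 6, PD**: an increase of 20% or more and "at least 5 mm absolute increase relative to nadir (minimum recorded tumor burden".
- **Text below Table 7**: "Determination of best overall response is based on changes in total tumor burden from the baseline (nadir, for PD) tumor assessment".
- **Confirmation of Disease Progression**: compares total burden with nadir, for both the 20% and the 5 mm, at two consecutive assessments.

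On the size of new lesions, Follow-up Assessment of Tumor Lesions counts non-nodal lesions from 10 mm upward, then adds a second limb where "the short axis is ≥ 15 mm for non-nodal lesions". For a new resected node, "it should be reported as a new non-measurable lymph node if its short axis was < 15 mm".

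SAP Section 6 derives BOR from the investigator's assessment under Appendix D. Its DOR, TTP and PFS definitions use PD on the same criteria. None of them states the reference point.

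**The concern.** Table 7 is the matrix that assigns the response at each assessment. Read as written, its PD row starts at 20% above baseline. In a subject whose tumor has shrunk, burden can then regrow well past 20% above nadir while the matrix still returns PR or SD. Table 6 calls the same scan PD.

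Two sites, or a site and a programmer, could therefore follow Appendix D faithfully and record different visit responses. The affected endpoints are BOR and ORR (whether a response is confirmed) and DOR, TTP and PFS (the date of PD). Nadir is the minimum recorded burden, so it cannot exceed baseline. The matrix therefore dates PD the same as Table 6 or later, never earlier, and the bias lengthens the time-to-event endpoints.

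Confirmed PD per the same criteria is also one of the reasons for ending treatment (Protocol Sections 6.2.1.1 and 6.2.1.3), so the conflict is not confined to reporting.

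**Working it through.** The plan gives no figure to reproduce. The check applies both rules to the same burdens. The thresholds (30% decrease, 20% increase, 5 mm) are the documents'; the burdens are assumed for illustration.

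Let B be baseline, N nadir and X the current burden.

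- Table 7 with footnotes a and e: PR if X ≤ 0.7B; PD if X ≥ 1.2B and X − N ≥ 5 mm; SD between.
- Table 6: PR if X ≤ 0.7B; PD if X ≥ 1.2N and X − N ≥ 5 mm.

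**Thresholds at B = 100, N = 50.** Table 6 PD starts at 1.2 × 50 = 60 mm (rise 10 mm, so the 5 mm part is met). Table 7 gives PR up to 0.7 × 100 = 70 mm, SD from there to below 120 mm, and PD from 1.2 × 100 = 120 mm. The two PD thresholds differ by a factor of two.

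**Individual scans**

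| B, N, X (mm) | Change from B | Table 7 | Change from N | Table 6 |
|---|---|---|---|---|
| 100, 50, 65 | −35% | PR | +30%, +15 mm | PD, and also PR |
| 100, 60, 80 | −20% | SD | +33.3%, +20 mm | PD |
| 100, 90, 110 | +10% | SD | +22.2%, +20 mm | PD |

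**Where the conflict arises.** PR against PD needs 1.2N ≤ 0.7B, so N ≤ 0.7/1.2 = 58.3% of baseline, plus the 5 mm rise. SD against PD can arise after smaller shrinkage, as the third row shows. If burden has never fallen below baseline, N = B and the rules agree.

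**Table 6 alone does not settle the first row.** At 65 mm the burden is 35% below baseline (PR) and 30% above nadir (PD). No precedence is stated.

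**Table 7 is also uneven within itself.** At B = 100 and N = 50, a measured sum of 65 mm is PD under footnote g if another lesion could not be evaluated, but falls in the PR row if the assessment is complete.

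**Effect on ORR.** Take burdens of 100, 50 and 65 mm, with the last two scans at least 28 days apart. The matrix gives PR then PR, a confirmed response. The nadir rule, with PD taken over PR, gives PR then PD, which SAP Table 3 scores as a BOR of SD. One subject is 1/24 = 4.2 to 1/18 = 5.6 percentage points, and more if subjects without measurable disease at baseline are excluded.

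**New-lesion size.** Footnote a uses strictly more than 10 mm; the follow-up text uses 10 mm or more. With 50 mm unchanged and a new non-nodal lesion of exactly 10 mm, burden is 60 mm (+20%, +10 mm): PD if counted, SD if not.

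**The case against.** The strongest reply is that the intended rule is plain. Footnote e brings nadir into the PD row, footnote g uses it for both parts, the sentence under the table names nadir for PD, and the confirmation and resection texts repeat it. Every PD statement that names its own reference uses nadir, and footnote a is a general column note. This stands as evidence of intent. It also rules out an inference a reader might draw, that Table 7 measures all change against baseline.

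It does not remove the conflict. Footnote e leaves the 20% where footnote a put it, footnote g covers only incomplete visits, and the nadir sentence concerns best overall response. The next sentence keeps subjects as PR or SD if they meet the Table 7 thresholds. The confirmation rule begins only once a visit has been classed as PD, so a visit that the matrix calls PR never reaches it.

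A second tempting reading is that footnote a admits every new lesion above 10 mm, including small nodes. On that reading, a stable 60 mm burden plus a new 12 mm short-axis node becomes 72 mm (+20%, +12 mm), PD instead of SD. The documents do not support this: the footnote is limited to measurable lesions, and Appendix D elsewhere sets 15 mm short axis for measurable nodes. The 15 mm limit is in the text, not in Table 6. The second non-nodal label is an apparent slip, since Appendix D measures short axis only for nodes. These are editorial points.

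It is also fair that the affected endpoints are secondary and descriptive, that later PD does not undo a response already confirmed, and that the documents do not show how many subjects would fall in the disputed range.

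**Conclusion.** The conflict over the reference for the 20% is real and more than clerical, because following the matrix as written can misclassify visits that feed BOR, ORR, DOR, TTP and PFS. It should be corrected. The primary endpoint, incidence of DLTs, is untouched.

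For a subject with baseline 100 mm and nadir 50 mm, the PD threshold is 60 mm or 120 mm depending on the table. These burdens are assumptions; the gap is 1.2 × (B − N) wherever the 5 mm condition is already met, and vanishes when burden never falls below baseline. The effect on the trial's actual estimates cannot be given from the documents. It depends on how many subjects shrink and then regrow, and on which table the sites used.

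**What to change.** 1. Reconcile Table 7 footnotes a and e with Table 6, the best-overall-response sentence and the confirmation text, so that one reference point for the 20% increase applies in endpoint derivation. The other explicit PD statements in Appendix D use nadir.
2. State which category applies when a burden meets both a PR or SD row and the PD criterion.
3. State the same reference in the SAP definitions of BOR, DOR, TTP and PFS.
4. Editorial: align the new-lesion size in footnote a with the measurable-lesion definitions, including the nodal limit and the 10 mm boundary, and correct the second non-nodal label in the follow-up text.

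Confirmed PD also ends treatment, so the sponsor must reconcile the passages for that use as well. No stopping rule is proposed here.

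The cost is wording in Appendix D and the SAP, a clarification to sites, and a check of visits already assessed (11 subjects were enrolled at the time of Amendment 3). No new data are needed.

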Clinical lesions will only be considered measurable when they are superficial and ≥ 10 mm diameter as assessed using calipers (eg, skin nodules). For the case of skin lesions, documentation by color photography including a ruler to estimate the size of the lesion is suggested. As noted above, when lesions can be evaluated by both clinical exam and imaging, imaging evaluation should be undertaken since it is more objective and may also be reviewed at the end of the study

Ultrasound:

Ultrasound should not be used as a primary method to assess lesion measurements in response to treatment. If new lesions are identified by ultrasound in the course of the study, confirmation by CT or MRI is advised.

At baseline, lesions are categorized as measurable or non-measurable according to the following definitions:

Measurable Lesions:

Measurable lesions are defined at baseline as lesions that can be accurately measured in at least one dimension (ie, longest diameter for non-nodal lesions and short axis for lymph nodes will be measured and followed) with a minimum size of:

- ≥ 10 mm by CT scan (CT scan slice thickness no greater than 5 mm) or MRI
- ≥ 10 mm caliper measurement by clinical exam for superficial cutaneous or subcutaneous melanoma lesion as measured by caliper
- A lymph node must be ≥ 15 mm in short axis when assessed by CT scan or MRI.

Target lesions must not be chosen from a previously irradiated field unless there has been documented tumor progression in that field prior to enrollment. The distribution of the target lesions should be representative of the subject's overall disease (eg, largest lesions per organ).

Non-Measurable Lesions:

All other lesions, including small lesions (longest diameter < 10 mm or pathological lymph nodes with ≥ 10 mm but < 15 mm short axis) and other truly non-measurable lesions are considered non-measurable and characterized as non-target lesions. This will include any measurable lesions beyond the maximum number of 10 total or 5 per organ at each time point that were not chosen as target lesions. Only cancerous lesions should be selected as non-measurable lesions and not indeterminate lesions and lesions that could be cancer. Other examples of non-measurable lesions include some bone

lesions*, leptomeningeal disease, inflammatory breast disease, lymphangitic involvement of the skin or (lymphangitis cutis/pulmonis), and groups of lesions that are small and numerous.

Fluid Collections

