If a target/new measurable lesion and a non-target/new non-measurable lesion merge, the non-target/new non-measurable lesion should be recorded as “absent” for the current and all future assessments while the target lesion/new measurable lesion should include both merged lesions for recording measurements.

Separating Lesions

When a target/new measurable lesion splits into 2 or more lesions, the largest measurable part of the split lesion should be considered to be the previously recorded target/new measurable lesion with measurements provided for the current assessment and followed for future assessments. The dimensions of the split parts would still be considered measurable. Any new lesions that result from separating should be documented and followed for future assessments as new measurable or non-measurable lesions that were generated by separating and not truly new lesions.

When a non-target/new non-measurable lesions splits into 2 or more lesions, the largest part of the split lesion should be considered to be the previously recorded non-target/new non-measurable lesion and followed as “present” for the current assessment and followed for future assessments. Any new lesions that result from separating should be documented and followed for future assessments as new non-measurable lesions that were generated by separating and not truly new lesions.

Approved

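### Appendix D's splitting rule lets parts of a split target lesion below 10 mm drop out of the tumor burden, so a low-burden subject whose lesion only fragments can be scored as a partial response

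*Protocol*

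**What the plan says.** Three sentences in Protocol Appendix D, Separating Lesions, govern the splitting of a target or new measurable lesion.

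- The record follows one part: "the largest measurable part of the split lesion should be considered to be the previously recorded target/new measurable lesion".
- The parts keep their status, with no size condition: "The dimensions of the split parts would still be considered measurable".
- The remaining parts are filed separately: "Any new lesions that result from separating should be documented and followed for future assessments as new measurable or non-measurable lesions that were generated". The sentence ends by labelling them as products of separation rather than genuinely new disease. It gives no criterion for choosing between the two filings.

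Other parts of Appendix D decide what each filing does.

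- The sum is defined as "Tumor Burden = sum of diameter of target lesions + sum of diameter of new measurable lesions". A new non-measurable lesion therefore adds 0 mm.
- New lesions count as measurable if they are ones "for which the longest diameter is ≥ 10 mm for non-nodal lesions". The baseline definition of non-measurable disease mirrors this: "All other lesions, including small lesions (longest diameter < 10 mm".
- PR is a fall in burden of at least "30% relative to baseline confirmed by a consecutive assessment at least 4 weeks (28 days) after first documentation".
- New lesions do not stand in the way: "Subjects are considered to have partial response (PR) or stable disease (SD) even if new lesions were present". Table 7 likewise accepts any status of new non-measurable lesions for PR; they block only CR.

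SAP Section 6 derives best overall response from investigator assessment under Appendix D and adds no rule for split lesions.

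**The concern.** The second and third sentences of the splitting paragraph do not fit together. If every part stays measurable, the option to file a part as non-measurable has no use. If parts are sorted by size, the statement that they are still measurable has no effect for the small ones. The two filings give different tumor burdens from one scan, and sorting by size removes tissue that was in the baseline sum.

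Elsewhere Appendix D avoids this. An intact non-nodal target that shrinks stays in the sum at its actual size, or at 5 mm if it is too small to measure. After resection of a lesion that contained cancer or had unknown pathology, response is unevaluable except for PD, so tissue taken out of the sum cannot create a response. Splitting has no such safeguard.

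What is at stake is a PR without shrinkage, which feeds ORR, DOR and TTR. The same event sets a nadir that is too low, and later PD calls for TTP and PFS are measured against it.

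**Working it through.** The plan gives no figure for split lesions, so there is none to reproduce. The check applies the plan's own rules to assumed splits.

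**Inputs from Appendix D.** Burden = targets + new measurable lesions. A new non-nodal lesion is measurable from 10 mm. PR is a change of −30% or lower from baseline. PD is an increase of at least 20% and at least 5 mm from nadir. PR and PD need confirmation at least 28 days later.

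**Assumption.** Part sizes are illustrative, and the parts' diameters add up to the original diameter, so nothing has shrunk. Real fragments need not add up this way.

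**Formula.** Change = (burden after − baseline) / baseline.

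| Baseline and split | All parts counted | Parts below 10 mm dropped |
|---|---|---|
| 30 mm → 21 + 9 | 30 mm, 0%, SD | 21 mm, −9/30 = −30.0%, PR |
| 36 mm → 18 + 9 + 9 | 36 mm, 0%, SD | 18 mm, −18/36 = −50.0%, PR |
| 33 mm → 24 + 9 | 33 mm, 0%, SD | 24 mm, −9/33 = −27.3%, SD |
| 30 mm → 21 + 9, plus another target of 20 mm | 50 mm, 0%, SD | 41 mm, −9/50 = −18.0%, SD |
| 36 mm → 18 + 9 + 9, plus another target of 20 mm | 56 mm, 0%, SD | 38 mm, −18/56 = −32.1%, PR |

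**Limit of the effect.** If k parts, each below 10 mm, are dropped from a total baseline burden B, the loss is below 10k mm. PR needs loss/B ≥ 0.30, so B must be below 10k/0.30: 33.3 mm for k = 1 and 66.7 mm for k = 2. Burdens this low are eligible, because inclusion criterion 106 asks for only one injectable lesion of at least 10 mm.

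**Confirmation.** A fragment still below 10 mm at the confirmatory scan is excluded again, so the 28-day rule does not remove the false PR.

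**Nadir.** In the first row the recorded nadir becomes 21 mm. If the 9 mm part grows to 10 mm it enters the sum: 21 + 10 = 31 mm, which is +10 mm and 10/21 = +47.6% from nadir and meets the PD threshold. With all parts counted throughout, the nadir is 30 mm and the change is +1 mm, 1/30 = +3.3%, SD.

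**Effect on ORR.** One false PR among 18 subjects moves ORR from 0/18 (exact 95% CI 0 to 18.5%) to 1/18 = 5.6% (0.1 to 27.3%). Among 24 it moves from 0% (0 to 14.2%) to 4.2% (0.1 to 21.1%). Protocol Section 10.4.2 and SAP Section 10.5.1 exclude subjects without baseline measurable disease where applicable, so the denominator may be smaller and the step larger.

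**The case against.** The best defence is that the text can be read without harm. If the sentence on measurable dimensions governs, every part is a new measurable lesion, all of it is counted, and no false PR arises. The other coherent reading sorts the parts by the ordinary size threshold; the reference to the largest measurable part suggests that some parts may not be measurable. This does not rescue the rule. Nothing in Appendix D chooses between the readings, and the size-sorting one is exactly the one that gives PR in the first row of the table.

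The defence is right about scale, and three stronger inferences should be resisted.

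- A reader might infer that any fragmenting target can become a PR. The arithmetic does not support this. One dropped part is not enough at a baseline of 33.3 mm or more, and other targets (up to 10 are summed) dilute the effect.
- A reader might infer that parts of 10 mm or more can also be filed as non-measurable, so that an even split of a large lesion would be a PR. The splitting sentence taken alone does not forbid it, but the size definitions elsewhere in Appendix D speak against it.
- A reader might infer that response rests on tumor burden alone. That is wrong for CR, which non-target and new non-measurable lesions block.

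It also stands that the documents give no evidence on how often injected lesions split, and that the only stated hypothesis concerns safety.

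**Conclusion.** The splitting paragraph is wrong as written, and the point is minor. It gives two tumor burdens for one scan, and under a natural reading it scores a lesion that has only fragmented as a PR and lowers the nadir. Without true shrinkage, and with only parts below 10 mm dropped, this is confined to subjects with a total baseline burden below 33.3 mm (one dropped part) or below 66.7 mm (two).

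The consequence falls on secondary efficacy endpoints: ORR, DOR and TTR directly, and TTP and PFS through the nadir. One case moves ORR by 4.2 to 5.6 percentage points if all 24 or 18 dosed subjects are in the denominator, well inside the width of the exact intervals. The primary DLT endpoint is unaffected. The conclusion about the wording rests on the text alone. The sizes rest on assumed fragment diameters, and how often this would happen is unknown and probably low.

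**What to change.** Rewrite the whole splitting paragraph for target and new measurable lesions. Its first sentence must change too, because it gives the target record to the largest part only and would contradict a rule that sums the parts. The new text should say:

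- For non-nodal lesions, the measured longest diameters of all parts, whatever their size, are summed and recorded under the original lesion. Parts are not entered as new measurable or new non-measurable lesions.
- The 5 mm default is used at most once per original lesion, and only when no part can be measured. Giving it to each fragment would create progression in a shrinking lesion: a 20 mm target reduced to 12 mm plus three unmeasurable specks would become 12 + 5 + 5 + 5 = 27 mm, which is +7 mm and 7/20 = +35%.
- For nodal lesions, the actual short axis is kept for each node, and the CR criterion of below 10 mm applies to each node. Two nodes of 8 mm each would otherwise be recorded as 16 mm, although both meet the criterion.

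With this rule, both PRs that arise from a single split lesion in the table (30 mm and 36 mm baselines) return to 0% and SD. The cost is one paragraph in Appendix D and matching tumor-assessment CRF instructions, with no additional imaging.
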